	APPENDIX 2: Consent Form.....	28
	References	32

LIST OF ABBREVIATIONS

AE	Adverse Event
CF	Cystic Fibrosis
CFFPR	Cystic Fibrosis Foundation Patient Registry
CFTR	Cystic fibrosis transmembrane conductance regulator
DSMB	Data Safety Monitoring Board
FDA	Food and Drug Administration
FEV₁	Forced expiratory volume in 1 second
GCP	Good Clinical Practice
HIPAA	Health Insurance Portability and Accountability Act of 1996
ICF	Informed Consent Form
IEC	Independent Ethics Committee
IPDAS	International Patient Decision Aid Standards
IRB	Institutional Review Board
LTx	Lung Transplant
PI	Principal Investigator
PrepDM	Preparation for Decision Making Scale
SAE	Serious Adverse Event
ToT	Take on Transplant
UNOS	United Network for Organ Sharing

PROTOCOL SYNOPSIS

TITLE	Lung Transplant READY (Resources for Education and Decision-making for Your CF) Pilot Study
SPONSOR	University of Washington
FUNDING ORGANIZATION	National Institutes of Health (NIH) - The National Heart, Lung, and Blood Institute (NHLBI)
NUMBER OF SITES	1
SPECIFIC AIMS	
 1. Determine whether Take on Transplant (online educational tool) improves patient preparedness for lung transplant (LTx) discussions using a pilot study that employs randomized, controlled, rollover trial design. 2. Longitudinally assess time spent using Take on Transplant through patient-level analysis of tool usage and identify predictors of increased usage.
RATIONALE	
 1. Despite therapeutic advances in CF care, many CF patients will go on to require LTx, including individuals already affected by advanced lung disease, those for whom highly effective CFTR modulators are not available or not tolerated, and for some despite CFTR modulators. Individuals with CF seek information about LTx and feel underprepared for the LTx decision. Use of a decision support tool or online educational materials about LTx may improve the quality, efficiency and effectiveness of LTx education in CF clinic and empower patients to engage in discussions about this complex medical treatment by increasing their sense of preparedness for the discussion. Feasibility must be established. The Preparation for Decision Making (PrepDM) Scale[1] is a validated measure of preparedness for decision making with known variance and high internal consistency (a 0.92-0.96), but it has not been studied in the CF population. Individual questions within the PrepDM Scale are informative and reflect IPDAS process measures[2, 3]. It is unclear whether there are ceiling or floor effects for particular questions within the PrepDM scale when evaluating a LTx decision support tool in the CF population, and the proposed pilot study utilizing a test-retest approach will establish preliminary means standard deviations, and reliability in this population. A prior decision aid for LTx in CF was shown to decrease decisional conflict in a randomized clinical trial and we will assess change in the Decisional Conflict Scale as a secondary endpoint.[4] 2. Engagement with Take on Transplant over time allows users to explore the content, potentially viewing more 'CF Stories', 'Resource Library', and 'Frequently Asked Questions' content and more interactions with 'My CF Stage'. Shared decision-making may naturally appeal to and benefit individuals who seek out health-related information, feel empowered to advocate for their own needs, and have more advanced educational attainment, while potentially increasing disparities for patients who are already disadvantaged. Shared decision making interventions

	tailored to disadvantaged groups can increase knowledge, informed choices and participation in decision-making, and reduce decisional conflict for patients in disadvantaged groups. We will obtain an individualized, longitudinal view of the participants' usage data as they interact with Take on Transplant, including page views and time spent per page, to characterize usage patterns over the 1 month. Characterization of different use patterns among individuals with disadvantaged backgrounds (oversampled in Aim 1) could inform enhancements to Take on Transplant to improve usage and acceptability by patients with limited access to LTx. Carefully assessing health literacy with the TOFHLA[5], an instrument that measures health-related reading comprehension and numeracy, could lead to understanding of mechanisms underlying differential use of Take on Transplant and change in PrepDM Scale.
STUDY DESIGN	This is a prospective, multi-center, randomized, controlled single-blind rollover pilot study
PRIMARY OBJECTIVE	To test feasibility and efficacy of Take on Transplant to improve patient preparedness for decision making about LTx.
SECONDARY OBJECTIVES	
 Understand LTx knowledge gained. Assess changes in decisional conflict. Measure changes in preparedness for LTx discussions. Assess changes in depression and anxiety symptoms. Longitudinally characterize time spent using Take on Transplant through analysis of patient-level usage data and determine whether ongoing use of the tool is associated with maintaining or increasing ratings of preparedness at 1-month. Identify baseline demographic and health literacy predictors of increased Take on Transplant usage Analyze interview transcripts to inform revision of Take on Transplant prior to a large randomized controlled trial
NUMBER OF SUBJECTS	~50
SUBJECT SELECTION CRITERIA	
Inclusion Criteria:
 
 Diagnosis of CF Adult, greater than or equal to 18 years of age Able to read and understand English, but English can be a second language Forced expiratory volume in one second (FEV₁) less than 50% predicted 
Exclusion Criteria:
 
 Previously underwent LTx
INTERVENTION ARM	Take on Transplant – Educational website that couples real-life CF patient experiences of LTx in the form of personal narratives with up-to-date, CF-specific, and guideline-based medical information about LTx.
CONTROL ARM	UNOS.org – Educational website that contains general information about transplantation (all organs).

DURATION OF SUBJECT PARTICIPATION AND DURATION OF STUDY	Subjects will be on study for up to 4 weeks with a total of three study sessions: Introduction Session, 2-Week Follow-up Session, and 4-Week Follow-up Session.
PRIMARY ENDPOINT	
The co-primary endpoint is feasibility, which will be defined as successful by 90% of enrolled participants completing the 2-week study visit.
 
The co-primary endpoint is an intention-to-treat assessment of the difference in mean PrepDM Scale in the intervention versus control arms of the study at the 2-week study visit.

SECONDARY ENDPOINTS	
 Difference in mean confidence-weighted true false (CTF) knowledge score will be measured in the intervention versus control arms of the study. CTF scoring adds points for certainty in correct responses and deducts points for certainty in incorrect responses. Participants receive +2 points when "sure" about a correct response, +1 if unsure about a correct response, -1 if unsure about an incorrect response and -2 if sure about an incorrect response. For a 14-item knowledge test, the maximum score is +28 and the minimum score is -28, with higher scores indicating more knowledge about lung transplant. Decisional Conflict Scale change will be measured from the baseline study visit to the 2-week study visit. The intention-to-treat analysis will compare mean change in the Decisional Conflict Scale between the intervention and control arms of the study. Scores range from 0 [no decisional conflict] to 100 [extremely high decisional conflict]. Likert rating of preparedness will be measured at the 2-week study visit (0=Don't know, 1= Not at all prepared, 2 = A little prepared, 3 = Moderately prepared, 4 = Very prepared). The intention-to-treat analysis will compare mean Likert-scale rating between the intervention and control arms of the study. PHQ-9 is a scale that measures symptoms of depression in the prior 2 weeks on a 0-27 scale, with higher scores indicating worsening depression and a score of 10 or higher consistent with a diagnosis of depression. Investigators will assess the difference in mean PHQ-9 score in the intervention versus control arms of the study at the 2-week study visit. Investigators will also determine the proportion with new PHQ-9 score greater than or equal to 10 in each arm. GAD-7 is a scale that measures symptoms of anxiety in the prior 2 weeks on a 0-21 scale, with higher scores indicating worsening anxiety and a score of 10 or higher consistent with a diagnosis of generalized anxiety disorder. Investigators will assess the difference in mean GAD-7 score in the intervention versus control arms of the study at the 2-week study visit. Investigators will also determine the proportion with new GAD-7 score greater than or equal to 10 in each arm. Longitudinally characterize time spent using Take on Transplant through analysis of patient-level usage data. Average

	
time spent using the research website from baseline to 2 weeks will be compared across study arms. Further, time spent using the investigator-designed website will be assessed as a predictor of:
 
1. change in CTF knowledge about LTx (14-question investigator-designed survey) from baseline to 2-week study visit,2. change in Likert preparedness from baseline to 2-week study visit,3. change in Decisional Conflict Scale from baseline to 2-week study visit, and4. mean PrepDM Scale at 2-weeks. 
• The PrepDM Scale will be measured for all participants with respect to Take on Transplant and mean score will be compared for participants in the intervention (4 weeks of exposure) versus control arms (2 weeks of exposure). PrepDM scores range on a scale from 0 to 100 with higher scores indicating a higher perceived level of preparation for decision making.• Identify baseline demographic and health literacy predictors of increased tool usage.
--	---

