1.3. Objectives of the clinical investigation

1.3.1. Primary objective

The primary research objectives are to pilot test feasibility and efficacy of ToT to improve patient preparedness for decision making about LTx. The co-primary endpoint is feasibility, which will be defined successful by 90% of enrolled participants completing the 2-week study visit. A co-primary endpoint is an intention-to-treat assessment of the difference in mean PrepDM Scale in the intervention versus control arms of the study at the 2-week study visit.

1.3.2 Secondary objective(s).

The secondary objectives are to:

- Understand LTx knowledge gained.
- Assess changes in decisional conflict.
- Measure changes in preparedness for LTx discussions.
- Assess changes in depression and anxiety symptoms.
- Longitudinally characterize time spent using ToT through analysis of patient-level usage data and determine whether ongoing use of the tool is associated with maintaining or increasing ratings of preparedness at 1-month.
- Identify baseline demographic and health literacy predictors of increased ToT usage
- Analyze interview transcripts to inform revision of ToT prior to a large randomized controlled trial

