1.4 Anticipated duration of the clinical investigation

The total duration of the clinical investigation is expected to be approximately 4 weeks: 2 weeks randomized to one arm of the study and 2 additional weeks with access to both websites.

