2.4.2 Anticipated number of research subjects

The study will enroll approximately 50 adults with CF and an FEV₁<50% predicted, without prior LTx. Individuals will be recruited from the University of Washington and collaborating adult CF centers across the United States.

We anticipate 90% (45 participants) of enrolled participants will complete the 2-week study visit.

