Research website – Participants will be introduced to the research website during the baseline session (V1). The research website is a portal that will contain links to two interventions including ToT and an attention control (unos.org). Before accessing the research website during the baseline session, participants will be randomized to first receive access to only one of the two websites through the portal. The research website will track website usage (i.e. time spent, content accessed, etc.) for all study participants for both ToT and unos.org. Once the participant completes the 2-week study visit (V2), the portal will contain access to both ToT and unos.org for the remainder of the study (2 more weeks).

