2.5.3 Allocation to treatment arms

Participants will be randomized 1:1 to either the intervention (“Take on Transplant”) or the attention control (unos.org), stratified by $FEV_1 < 30\%$ versus 30-50%. Participants will be given access to their assigned website via the research website portal for two weeks. After the 2-week session interview, access to the opposite arm assignment will be unlocked and participants will have unlimited access to both the intervention (ToT) and the attention control (Unos.org).

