- GAD-7 is a scale that measures symptoms of anxiety in the prior 2 weeks on a 0-21 scale, with higher scores indicating worsening anxiety and a score of 10 or higher consistent with a diagnosis of generalized anxiety disorder. Investigators will assess the difference in mean GAD-7 score in the intervention versus control arms of the study at the 2-week study visit. Investigators will also determine the proportion with new GAD-7 score greater than or equal to 10 in each arm.
- Longitudinally characterize time spent using Take on Transplant through analysis of patient-level usage data. Average time spent using the research website from baseline to 2 weeks will be compared across study arms. Further, time spent using the investigator-designed website will be assessed as a predictor of: 1. change in CTF knowledge about LTx (14-question investigator-designed survey) from baseline to 2-week study visit, 2. change in Likert preparedness from baseline to 2-week study visit, 3. change in Decisional Conflict Scale from baseline to 2-week study visit, and 4. mean PrepDM Scale at 2-weeks.
- The PrepDM Scale will be measured for all participants with respect to Take on Transplant and mean score will be compared for participants in the intervention (4 weeks of exposure) versus control arms (2 weeks of exposure). PrepDM scores range on a scale from 0 to 100 with higher scores indicating a higher perceived level of preparation for decision making.
- Identify baseline demographic and health literacy predictors of increased tool usage.

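### The synopsis promises test-retest reliability for PrepDM, but the rollover design provides no clean retest

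*Combined protocol and SAP*

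**What the plan says.** The synopsis rationale notes that PrepDM has not been studied in cystic fibrosis (CF), cites an internal consistency of 0.92 to 0.96 from elsewhere, and adds: "It is unclear whether there are ceiling or floor effects for particular questions within the PrepDM scale". It then says that "the proposed pilot study utilizing a test-retest approach will establish preliminary means standard deviations, and reliability in this population".

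Access is set out in three places. Section 2.5.2 says that at the baseline session (V1) "participants will be randomized to first receive access to only one of the two websites through the portal". Section 2.5.3 says that after the 2-week interview (V2) "access to the opposite arm assignment will be unlocked". Section 1.4 sums up the schedule as "2 weeks randomized to one arm of the study and 2 additional weeks with access to both websites".

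Section 2.6.1 adds a secondary endpoint: "The PrepDM Scale will be measured for all participants with respect to Take on Transplant", comparing 4 weeks of exposure in the intervention arm with 2 weeks in the control arm.

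Section 2.6.3 names PrepDM twice: in the co-primary regression at 2 weeks, and in exploratory usage models at the 2-week and 4-week visits. It contains no test-retest, internal-consistency, or floor and ceiling analysis.

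**The concern.** A test-retest coefficient estimates reliability when the same object is rated twice and nothing that should move the rating happens in between. A rollover design changes what participants can see between visits, so the protocol claims a property that its design does not have.

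The practical risk lies downstream. Section 2.6.3 says the data will inform a larger trial. An agreement figure from V2 and V3, labelled test-retest reliability, could be carried into that trial's planning as if it described measurement error alone. The rationale's floor and ceiling question can be answered from the planned data, but no analysis has been set down to answer it.

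**Working it through.** **1. The plan's own figure.** Section 2.6.2 gives a 95% CI of 79-96% for 90% of 50. The Wilson interval for 45/50 is 78.6% to 95.7%, so it reproduces. The documents give no precision target for reliability.

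**2. Numbers per arm.** Section 2.4.2: "We anticipate 90% (45 participants) of enrolled participants will complete the 2-week study visit". Allocation is 1:1 (section 2.5.3), so 45/2 gives 22 or 23 per arm at V2. Retention to the 4-week visit (V3) is not stated.

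**3. The visit pairs.**

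| Pair | Control arm | Intervention arm |
|---|---|---|
| V2 to V3 | unos.org after 2 weeks, then ToT after 2 weeks | ToT after 2 weeks, then ToT after 4 weeks with unos.org added |
| V1 to V2, if PrepDM is given at V1 after the introduction | unos.org after a brief introduction, then after 2 weeks | ToT after a brief introduction, then after 2 weeks |

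The control entry for V2 to V3 is an inference. Through the portal, controls have had only unos.org by V2, and 2 weeks of ToT exposure is reached at V3. The second row is conditional because section 2.5.2 only lists instruments that the surveys may contain. Appendix 1 caps the introduction at 10 minutes plus a demo video. If PrepDM were given before the introduction, V1 to V2 would straddle first access.

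**4. What a V2-V3 coefficient would measure.** Take the intervention arm, where the rated website is the same. Set the V2 variance to 1 and true reliability to 0.80. Let true scores change independently with variance *c*, and let the mean shift by *d* SD. Then

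agreement ICC = 0.80 / [(2 + *c*)/2 + *d*²/2].

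- *c* = 0, *d* = 0: 0.80/1 = 0.80
- *c* = 0.2, *d* = 0.3: 0.80/(1.1 + 0.045) = 0.70
- *c* = 0.4, *d* = 0.5: 0.80/(1.2 + 0.125) = 0.60

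Measurement error is the same in all three. The values of *c*, *d* and 0.80 are assumptions; the documents give none. Remembered answers push the coefficient up, so it is not a bound on reliability in either direction.

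**5. Precision of that coefficient.** For a one-way ICC with two ratings, F = (1 + r)/(1 - r). With n = 22 and r = 0.80, F = 9. The lower limit uses 9/2.373 = 3.79, giving 2.79/4.79 = 0.58. The upper uses 9 × 2.394 = 21.5, giving 20.5/22.5 = 0.91. The interval 0.58 to 0.91 covers the whole range in step 4, so the data could not separate poor reliability from real change.

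**6. What one visit can support, per arm (n = 22).**

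- Cronbach's alpha, Feldt interval: 1 - (1 - alpha) × F quantile on 21 and 21(k - 1) df. The item count k is not in the documents. With k = 8, alpha 0.92 gives 1 - 0.08 × 1.785 = 0.86 to 1 - 0.08 × 0.476 = 0.96, and alpha 0.96 gives 0.93 to 0.98. Taking k = 12 moves a limit by at most 0.003.
- Proportion of responses at an item's extreme, Wilson: half-width at most 19 percentage points. If nobody is at the extreme, the upper limit is 3.84/(22 + 3.84) = 15%.

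**The case against.** The strongest reply is that this is one clause in the rationale. Reliability is not a specific aim, objective, endpoint or basis for the sample size. Means and standard deviations, two of the three promised quantities, come from planned data. Alpha and percentages at the extremes are routine descriptives that nobody needs permission to report. All of this stands and keeps the point minor. Silence in section 2.6.3 would on its own be no more than missing detail. What remains is that the rationale names a method, test-retest, that the design does not provide.

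Two stronger readings are tempting, and the documents do not support them.

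- A reader might infer that no participant can ever rate the same website twice under unchanged access. The documents do not fix whether PrepDM is given at V1, and the design schematic is not shown in the text available. A V1 rating after the introduction would share assigned-site-only access with V2. It would still compare minutes of exposure with two weeks, so it would be an imperfect retest.
- A reader might infer that the plan expects PrepDM to change between V2 and V3, because section 1.3.2 aims to "determine whether ongoing use of the tool is associated with maintaining or increasing ratings of preparedness at 1-month". That wording allows for no change, and it may refer to the separate Likert preparedness rating. It shows that the plan does not assume stability, and no more.

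**Conclusion.** The point holds as a minor inconsistency. The rationale claims test-retest reliability, and the only pair of visits for which the analysis plan names PrepDM straddles the unlocking of the second website. The rated website stays the same in only one arm, about 22 or 23 expected V2 completers, and there exposure doubles and a second website is added. A V2-V3 coefficient should therefore not be reported as test-retest reliability. The fall from 0.80 to as low as 0.60 illustrates the mixing under assumed values and is not a prediction.

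The conclusion rests on the access schedule, which is explicit, and on the inference that controls rate unos.org at V2 and ToT at V3. It would not be right to conclude that the pilot's main result is compromised: the between-arm comparison at V2 uses one rating per participant and does not depend on a retest.

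**What to change.** 1. In the synopsis rationale, drop the test-retest wording. Say instead that the pilot *will establish preliminary means, standard deviations, internal consistency and item-level floor and ceiling rates*.
2. In section 2.6.3, add: *For PrepDM, the mean, SD, Cronbach's alpha and, for each item, the proportion at the lowest and at the highest response will be reported with 95% CIs, by arm and by website rated, at V2 and for the ToT-referenced rating after rollover. Ratings of ToT and unos.org will not be pooled.* Including the later rating matters because, on the inferred schedule, that is when controls first rate ToT.
3. If an intervention-arm V2-V3 coefficient is reported, call it *agreement under continued exposure*.

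The cost is a reworded clause and a short addition to the analysis plan, using data from surveys already planned. The pilot gives up a test-retest figure, and internal consistency does not replace it because it says nothing about stability over time. If the sponsor wants a retest, it would need a repeat rating of the same website, after comparable exposure and before the unlock. That is an extra contact which the three-session schedule in section 2.5.9 does not contain.

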1.0 PURPOSE OF THE INVESTIGATION

1.1. Name of intervention

Take on Transplant (ToT): an educational website that couples real-life CF patient experiences of LTx in the form of personal narratives with up-to-date, CF-specific, and guideline-based medical information about LTx.

1.2. Intended use of the intervention

ToT addresses patient-identified knowledge gaps and provides personalized educational content to help CF patients prepare for LTx discussions and decisions.

1.3. Objectives of the clinical investigation

1.3.1. Primary objective

The primary research objectives are to pilot test feasibility and efficacy of ToT to improve patient preparedness for decision making about LTx. The co-primary endpoint is feasibility, which will be defined successful by 90% of enrolled participants completing the 2-week study visit. A co-primary endpoint is an intention-to-treat assessment of the difference in mean PrepDM Scale in the intervention versus control arms of the study at the 2-week study visit.

1.3.2 Secondary objective(s).

The secondary objectives are to:

- Understand LTx knowledge gained.
- Assess changes in decisional conflict.
- Measure changes in preparedness for LTx discussions.
- Assess changes in depression and anxiety symptoms.
- Longitudinally characterize time spent using ToT through analysis of patient-level usage data and determine whether ongoing use of the tool is associated with maintaining or increasing ratings of preparedness at 1-month.
- Identify baseline demographic and health literacy predictors of increased ToT usage
- Analyze interview transcripts to inform revision of ToT prior to a large randomized controlled trial

